9.1.2.4. Adverse Events

Partial dates will be imputed for adverse event start dates. Imputed dates will be kept in the final derived datasets. The start and stop dates as reported in the electronic case report form (eCRF) will be presented in the data listings.

Partial or missing AE start dates will be handled as follows:

- If the AE start date year value is missing, the date uncertainty is too high to impute a rational date. Therefore, if the AE year value is missing, the imputed AE start date is set to NULL.
- If the AE start date year value is less than the treatment start date year value, the AE started before treatment. Therefore:
 - If AE month is missing, the imputed AE start date is set to the mid-year point (01JulYYYY).

- Else if AE month is not missing, the imputed AE start date is set to the mid-month point (15MONYYYY).
- If the AE start date year value is greater than the treatment start date year value, the AE started after treatment. Therefore:
 - If the AE month is missing, the imputed AE start date is set to the year start point (01JanYYYY).
 - Else if the AE month is not missing, the imputed AE start date is set to the later of (month start point (01MONYYYY), AE start reference date + 1 day).
- If the AE start date year value is equal to the treatment start date year value:
 - And if the AE month is missing the imputed AE start date is set to the AE reference start date + 1 day.
 - Else if the AE month is less than the treatment start month, the imputed AE start date is set to the mid-month point (15MONYYYY).
 - Else if the AE month is equal to the treatment start date month or greater than the treatment start date month, the imputed AE start date is set to the later of (month start point (01MONYYYY), AE start reference date + 1 day).

Any AE with a missing start date will be considered a treatment emergent event, as defined in Section 9.3.2.

- Partial or missing AE stop dates will be handled as follows:
- If a day is missing, then the day will be set to the last day of the month.
- If a day and month are missing, then the date will be set to December 31st.
- However, if the imputation results in a date that is after the date of the last dose of study treatment, then the date of the last dose will be used as the imputed AE stop date.

Start or end dates which are completely missing (i.e. no year specified) will remain missing, with no imputation applied.

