9.3.2. Therapy Periods

For classifying AEs, infections, injection site reactions, cardiac events, liver events, medications, and non-drug therapies, the therapy periods will be defined as:

- **Pre-therapy:** If the onset date of the event is before the start date of study medication, the event will be considered pre-therapy. If the onset date of the event is on the start date of study medication, the event will be considered as on-therapy.
- **On-therapy (Treatment-emergent):** If the onset date of the event is on or after the start date of study medication and on or before 4 weeks after the date of last dose, the event will be considered on-therapy.

- **Follow-up:** For all subjects who do not enter the Individualized Follow-up Period, if the onset date of the event is after 4 weeks after the date of last dose, the event will be considered a follow-up event.
- **Individualized Follow-up:** For all subjects identified as entering the Individualized Follow-up period, events with an onset date after 4 weeks after the date of last dose will be considered individualized follow-up events.

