12.2. Adverse Events

AEs will be collected from the start of study treatment (treatment emergent AEs) through the follow-up contact.

SAEs will be collected over the same time period as stated above for AEs. However, any SAEs assessed as related to study participation (e.g., study treatment, protocol-mandated procedures, invasive tests, or change in existing therapy) or related to a concomitant medication, will be recorded from the time a subject consents to participate in the study up to and including any follow up contact.

AEs will be categorized by their occurrence in regard to therapeutic period (pre-therapy, on-therapy, follow-up or individualized follow-up) as defined in Section 9.3.2. Any events that occur prior to initiation of investigational product will be reported as medical history. If, however, a prior event is reported on the AE page of the eCRF it will be reported as 'pre-therapy' AE. Pre-therapy AEs will be presented only in data listings and will not be summarized.

All AEs will be coded using Medical Dictionary for Regulatory Activities (MedDRA) and summarized based on system organ class (SOC) and PT. Summaries by treatment group of the number and percentage of subjects with an AE will be presented in alphabetical order by SOC. Within the SOC level, the PTs will be presented in descending order of incidences. A PT will not be presented if no AEs occur within the level.

An overview summary of the number and percentage of subjects with any AE and the total number of AEs recorded during the randomized treatment period will be presented by treatment group. For the AEs recorded in the follow-up (FU) period if there are not enough events to summarize (i.e. <10 events) then the data of those AEs will be listed only otherwise it will be summarized. If any AEs recorded in the individualized follow-up period it will be listed only.

For AE listings, AE duration will be defined as (the date of resolution of the AE – the onset date of the AE) + 1 day. If no date of resolution is provided, AE duration will be presented as 'Continuing'.

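### The SAP caps imputed AE stop dates at the last dose, so an AE that starts after the last dose and has a partial stop date is given a stop date before its onset

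*SAP*

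**What the plan says.** The stop-date rule in SAP 9.1.2.4 has three steps.

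- Day missing: "If a day is missing, then the day will be set to the last day of the month".
- Day and month missing: "If a day and month are missing, then the date will be set to December 31st".
- Override, where the completed date is later than the final dose: "then the date of the last dose will be used as the imputed AE stop date".

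The rule reaches only stop dates with a known year: "Start or end dates which are completely missing (i.e. no year specified) will remain missing, with no imputation applied". The same section keeps imputed dates in the final derived datasets and shows the eCRF dates, as reported, in the listings.

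SAP 9.3.2 assigns each AE to a period by its onset date. An onset from the start of study medication is treatment-emergent if it falls "on or before 4 weeks after the date of last dose, the event will be considered on-therapy". For subjects in Individualized Follow-up, "events with an onset date after 4 weeks after the date of last dose will be considered individualized follow-up events"; for the others, later onsets are follow-up events.

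In SAP 12.2, for listings, "AE duration will be defined as (the date of resolution of the AE" minus the onset date), plus 1 day. An AE with no resolution date is shown as continuing.

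**The concern.** The cap treats the last dose as the latest date on which an AE can end. The plan's own period definitions do not: they provide for AEs that begin after the last dose, and such an AE cannot have resolved on or before it. For these AEs the rule does more than lose precision; it produces an impossible date.

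A second effect concerns AEs that begin during treatment. If the site recorded resolution in a month or year later than that of the last dose, the cap replaces known information with a date that contradicts it. Filling in a missing day should not change the reported month.

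At stake are the accuracy of AE stop dates in the derived datasets and, depending on how the SAP is programmed, the AE durations in the listings.

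**Working it through.** The plan states no figure to reproduce, so the check applies the rule as written.

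**Inputs**

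- Imputation and cap: SAP 9.1.2.4.
- On-therapy window, last dose + 4 weeks (28 days), with later onsets still classified: SAP 9.3.2.
- Duration = stop − onset + 1 day: SAP 12.2.
- AEs are collected after the last dose. The last planned dose is at Week 56 and the core period ends at Week 60 (Protocol 3.1). Individualized Follow-up can run to 2 years after the last dose (Protocol 3.1.3). Protocol 6.3.7 and the footnote to Protocol Table 6-2 differ on which AEs are collected there, but both collect some.
- Assumed for illustration only: last dose on 10 March 2016.

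**Onset after the last dose**

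Let L be the last dose date, and let onset be L + k with k ≥ 1. The AE resolves no earlier than onset, so the end of its reported stop month or year is also after L. The cap therefore always applies and stop = L.

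Duration = L − (L + k) + 1 = 1 − k days.

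| k (days after last dose) | Imputed duration (days) |
|---|---|
| 1 | 0 |
| 2 | −1 |
| 10 | −9 |
| 28 (end of on-therapy window) | −27 |
| 730 (2 × 365) | −729 |

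In study days, with last dose on Day 85 and onset on Day 100: 85 − 100 + 1 = −14.

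The rule was also run for every onset from 1 to 730 days after the last dose, with resolution 0, 3, 10 or 40 days after onset and only the day of the stop date missing: 730 × 4 = 2,920 cases. All 2,920 gave a stop date before onset. In the 4 cases with k = 1 the duration was 0; in the rest it was negative.

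**Worked dates, with and without the cap**

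| Onset | Reported stop | With cap | Without cap |
|---|---|---|---|
| 20 Mar 2016 | Mar 2016 | 10 Mar, −9 days | 31 Mar, 12 days |
| 20 Mar 2016 | 2016 only | 10 Mar, −9 days | 31 Dec, 287 days |
| 5 Mar 2016 | May 2016 | 10 Mar, 6 days | 31 May, 88 days |
| 5 Mar 2016 | Mar 2016 | 10 Mar, 6 days | 31 Mar, 27 days |
| 5 Jan 2016 | Jan 2016 | 31 Jan, 27 days | 31 Jan, 27 days |

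The first two rows are impossible with the cap. The third contradicts the reported month. In the fourth, 10 March lies within the reported month, so the capped date is possible. The fifth is unaffected. The second row also shows why removing the cap needs another upper bound: a year-only stop would otherwise run to 31 December.

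**Which outputs use the stop date**

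- Therapy period and treatment emergence depend on onset only (SAP 9.3.2).
- AE and SAE tables count subjects and events by system organ class and preferred term (SAP 12.2 to 12.3).
- Duration is defined for AE listings only (SAP 12.2). A partial resolution date cannot enter that formula without imputation, and the SAP does not say whether the imputed date is used.

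**The case against.** The best defence is that almost nothing displayed depends on the imputed stop date. Listings show the date as the site recorded it, the incidence tables do not use stop dates, safety data undergo no inferential analysis, and AEs in Individualized Follow-up are listed only. An impossible value also needs three things together: onset after the last dose, a recorded resolution, and a stop date with the year known but the day or month missing. With 69 subjects randomized, there may be no such AE. All of this stands, and it limits the point to low impact. It does not make the rule right, because the imputed dates are kept in the derived datasets.

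A narrower objection also stands. Where an AE began on treatment and the reported stop month contains the last dose, the last dose date and the month end are both conventions, and neither is better evidenced. The truncation point therefore holds only where the reported stop month or year is later than that of the last dose.

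Capping at the last dose does prevent implausibly late year-end dates, but other bounds do this without contradicting onset. SAP 9.1.2.3 uses the same month-end and 31 December convention for medication stop dates with no last-dose cap, and the SAP gives no reason for treating AEs differently.

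**Conclusion.** The rule is wrong as written, with low impact. Every AE with onset after the last dose and a partial stop date (year known) receives a derived stop date k days before onset, and a duration of 1 − k days if the formula is applied to it. AEs that began on treatment and were reported as resolving in a month or year later than that of the last dose are cut off at the last dose. This assumes only that the text is programmed literally and that the reported stop month or year is not earlier than onset.

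The certain effect is wrong stop dates in the derived datasets. Wrong listed durations are conditional on the imputed date feeding the SAP 12.2 formula.

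A reader might infer more, and the documents do not support it:

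- That AE or SAE rates are affected. They are not, since they do not use stop dates.
- That late or prolonged infections will appear in listings to have resolved at the last dose. The listings show the eCRF dates.
- That subjects stopped early by the study's termination are hit most often. The documents give no count of partial stop dates, overall or by subgroup.

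**What to change.** In SAP 9.1.2.4, delete the last-dose cap. Impute the last day of the reported month, or 31 December if only the year is known. Bound this above by the earliest of last contact, death or data cut-off, keep it within the reported month or year, and never let it precede AE onset. In SAP 12.2, state which stop date, reported or imputed, is used for AE duration, and what is shown when the reported date is partial.

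The cost is a few sentences of SAP text and a small change to one derivation. No data collection and no incidence table is affected.

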9.1.2.5. Historical Information

For a stand-alone date of historical information (i.e. date of PV symptom onset, date of PV diagnosis, date of most recent failed steroid taper), a date with a missing day and month will be imputed as June 30th of the year. If the month is present but the day of the month is missing, then the day of the month will be imputed to be the 15th of the month.

9.1.3. Laboratory data

Some subjects may have the lab results values below the instrument detectable range like values with '<x.x' or '<x'. For such cases, the numeric values will be set as being half of

the instrument detect range. i.e., If the lab result value is “<14” then the numeric result value will be set to 7.

In some cases subjects may have the values above the instrument detectable range; like '>x.x'. In such cases the character value will just be set to numeric value after removing the '>' prefix. i.e., If the lab result value is “>100” then the numeric result value will be set to 100.

9.2. Derived and Transformed Data

9.2.1. Change from Baseline

The baseline value for an assessment is defined as the last non-missing value before the start of treatment. Change from Baseline is defined as the post-baseline value minus the baseline value for the given assessment. If either the baseline or post-baseline value is missing then the change from baseline value will also be missing.

9.2.2. Race

Using nine standard race categories in the eCRF, subjects are asked to provide all geographic ancestry (i.e. race) to which they identify.

These race categories include:

1. African American /African Heritage
2. American Indian or Alaska Native
3. Asian – Central/South Asian Heritage
4. Asian – East Asian Heritage
5. Asian – Japanese Heritage
6. Asian – South East Asian Heritage
7. Native Hawaiian or other Pacific Islander
8. White – Arabic/North African Heritage
9. White – White/Caucasian/European Heritage

Race will be summarized in the demography table for ITT population.

9.2.3. Time Since Pemphigus Vulgaris Symptom Onset and Diagnosis

The time (in years) since PV symptom onset is defined as: (date of randomization – date of PV symptom onset)/365.25.

The time (in years) since PV diagnosis is defined as: (date of randomization – date of PV diagnosis)/365.25.

PV history will be summarized in a table as per section [10.8](#).

9.2.4. Time Since Most Recent Failed Steroid Taper

The time (in years) since the most recent failed steroid taper that resulted in a disease flare/relapse at a prednisone/prednisolone dose >10 mg/day is defined as: (date of randomization – date of most recent failed steroid taper)/365.25.

9.2.5. Time to Remission on Minimal Steroid Therapy

Time to remission on minimal steroid therapy (in days) is defined as: ([date the subject initially tapered his/her oral prednisone/prednisolone dose to ≤10 mg/day and maintained ≤10 mg/day of oral prednisone/prednisolone with no new or nonhealing (established) lesions for ≥8 weeks by Week 60] – [date of randomization]) + 1 day. For subjects who experience more than one period of remission on minimal steroid therapy (i.e. a subject went into remission, then relapsed, and then went into remission again) time to remission on minimal steroid therapy is derived using a subject's first period of remission.

9.2.6. Time to Initial Flare/Relapse

Time to initial flare/relapse (in days) is defined as: [(time that ≥3 new lesions within 1 month appear and do not heal spontaneously within 1 week, or to the time when there is an extension of lesions that were present at the randomization visit) by Week 60 - date of randomization] + 1 day.

9.3. Assessment Windows

9.3.1. Study Day

When study day is used for display or in comparisons, the following algorithm will be used:

- study day = date of assessment - date of first dose + 1, if date of assessment ≥ first dose date
- study day = date of assessment - date of first dose, if date of assessment < first dose date.

Note that the date of first dose is Day 1 and the day before the date of first dose is Day -1 (there is no Day 0).

9.3.2. Therapy Periods

For classifying AEs, infections, injection site reactions, cardiac events, liver events, medications, and non-drug therapies, the therapy periods will be defined as:

- **Pre-therapy:** If the onset date of the event is before the start date of study medication, the event will be considered pre-therapy. If the onset date of the event is on the start date of study medication, the event will be considered as on-therapy.
- **On-therapy (Treatment-emergent):** If the onset date of the event is on or after the start date of study medication and on or before 4 weeks after the date of last dose, the event will be considered on-therapy.

- **Follow-up:** For all subjects who do not enter the Individualized Follow-up Period, if the onset date of the event is after 4 weeks after the date of last dose, the event will be considered a follow-up event.
- **Individualized Follow-up:** For all subjects identified as entering the Individualized Follow-up period, events with an onset date after 4 weeks after the date of last dose will be considered individualized follow-up events.

9.3.3. Visit Slotting Algorithm

For all safety and efficacy parameters to be summarized or analyzed by visit, data records will be slotted to one of the protocol specified visits using the following algorithm

- Determine the therapy period and study day for all records using the algorithms from Section 9.3.1 and Section 9.3.2.
- For all records (including unscheduled visit records, early withdrawal records and repeat visit records), use the therapy period and study day determined above with the slotting intervals in the analysis visit window table below to slot the record to the appropriate analysis visit.
 - For records determined to be during the pre-therapy period, the analysis visits will be based on the nominal visits recorded in the eCRF. The Baseline analysis visit will be assigned based on the study day slotting intervals as shown in the table below.
 - For records determined to be during the on-therapy period, use the study day with the slotting intervals in the table below to assign the records to the appropriate on-therapy analysis visit.
 - For records determined to be during the follow-up period, use the study day with the slotting intervals in the table below to assign the records to the appropriate follow-up period analysis visit.
 - For records determined to be during the individualized follow-up period, use the study day with the slotting intervals in the table below to assign the records to the appropriate individualized follow-up period analysis visit.

Table 9-1 Analysis Visit Windows

Scheduled Visit	Target Study Day of Visit	Slotting Intervals
Screening	-84 to -4	Not applicable
Baseline (Week 0)	1	-3 to 1 days
Week 2	15	2 to 22 days
Week 4	29	23 to 36 days
Week 6	43	37 to 50 days
Week 8	57	51 to 64 days
Week 10	71	65 to 78 days
Week 12	85	79 to 92 days
Week 14	99	93 to 106 days
Week 16	113	107 to 120 days
Week 18	127	121 to 134 days

Scheduled Visit	Target Study Day of Visit	Slotting Intervals
Week 20	141	135 to 148 days
Week 22	155	149 to 162 days
Week 24	169	163 to 176 days
Week 28	190	177 to 204 days
Week 32	218	205 to 232 days
Week 36	246	233 to 260 days
Week 40	274	261 to 288 days
Week 44	302	289 to 316 days
Week 48	330	317 to 344 days
Week 52	358	345 to 372 days
Week 56 *	386	373 to 400 days
Week 60** (End of Core Study Period) Subject has completed.	414	401 to 428 days

* Week 56 is the end of treatment visit for those subjects completing the study per protocol. For subjects who withdraw early from active treatment, the end of treatment visit will be assigned to an analysis visit based on the visit slotting algorithm using study day and therapy period.

** Week 60 is the follow-up visit for those subjects completing the study per protocol. Subjects completing the study and meeting all entry criteria will be offered the option to participate in an extension study, which will start after completion of the Week 60 visit.

For parameters that were not scheduled to be collected at all visits, yet values are available, the visit intervals defined in the table above will be used to slot records. As previously noted for the baseline record, the last non-missing value before the start of treatment will be used for analysis. For post-baseline records, for parameters collected multiple times within a slotting interval, the assessment taken closest to the target study day will be used for analysis/summarization.

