- e. Premedication: Each dose of study treatment will be preceded by acetaminophen/paracetamol and an antihistamine (see Section 5.1.2).
Postdose observation and medication: After the first dose, subjects should stay at the clinic to be monitored for any injection-related AEs for a minimum of 4 hours, with acetaminophen/paracetamol administered again at 4 hours. After subsequent doses, it is recommended that subjects stay at the clinic for a minimum of 1 hour, with acetaminophen/paracetamol self-administered approximately 4 to 6 hours after dosing if needed.
Note: An additional 20-mg loading dose (total of two 20-mg injections) will be administered at Week 0 and Week 4.
- f. Laboratory assessments include hematology, clinical chemistry, and urinalysis. "H" indicates visits with only hematology.
At Screening and Week 60/early withdrawal only—Hepatitis B, Hepatitis C, pneumococcal antibody assay, and toxoid antibody assay.
- g. Collect sample predose on dosing days.
- h. Informed consent must be obtained before collecting samples for optional testing (ie, pharmacogenetics research and pharmacokinetic-pharmacodynamic substudy analyses).
- i. Only sites preidentified to participate in pharmacokinetic-pharmacodynamic substudy. See Table 6-3 for the schedule of visits for sample collection.

Note: Visits from Week 2 through Week 60 to be scheduled within ±3 days of the specified time point. Visits during Individualized Follow-up to be scheduled within ±7 days.

Table 6-2 Time and Events Table: Individualized Follow-up Period

	As applicable ^a								Early WD
Study Week for Core Study Completers:	72	84	96	108	120	132	144	156	
Study Week for Early Withdrawals:	+12	+24	+36	+48	+60	+72	+84	+96	
Adverse events (including SAEs and AEs of special interest) ^b	X	X	X	X	X	X	X	X	X
Concomitant medications	X	X	X	X	X	X	X	X	X
Document steroid dose	X	X	X	X	X	X	X	X	X
Neurological symptoms questionnaire (PML monitoring)	X	X	X	X	X	X	X	X	X
PV lesion mapping	X	X	X	X	X	X	X	X	X
Pregnancy testing (urine) (women) – test monthly for 12 months after the last dose of ofatumumab SC; subjects may test at home during months without a clinic visit	X	X	X	X					X
Hematology	X	X	X	X	X	X	X	X	X
Clinical chemistry	X	X	X	X	X	X	X	X	X
IgG, IgM, IgA	X	X	X	X	X	X	X	X	X
Human anti-human antibody	X								X
Pharmacodynamic markers (flow cytometry)	X	X	X	X	X	X	X	X	X
HBV DNA – if applicable, test every 12 weeks for 6 months after the last dose of ofatumumab SC	PRN	PRN							PRN

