prednisone dose [<60 mg/day, ≥ 60 mg/day]) to receive SC administration of ofatumumab 20 mg or placebo once every 4 weeks (with an additional 20 mg 'loading' dose at both Week 0 and Week 4) for a total of 56 weeks (total of 17 injections across 15 monthly dosing visits). Two weeks after the first dose of ofatumumab SC or placebo (ie, Week 2), the oral steroid dose will be gradually reduced according to a fixed dose-taper schedule with a goal of reducing (ie, to ≤ 10 mg/day) or eliminating the dose of prednisone/prednisolone.

After the last dose of ofatumumab SC or placebo at Week 56, subjects will be followed-up for a minimum of 4 weeks, with a visit scheduled at Week 60. Subjects completing the study and meeting all entry criteria will be offered the option to participate in an extension study (OPV117059), which will start after completion of the Week 60 visit. If B-cell counts have not recovered by the Week 60 visit, subjects not entering the extension study will remain in an Individualized Follow-up Period until either the CD19+ B-cell counts or circulating IgG levels are \geq LLN or baseline levels (if $<$ LLN) or until 2 years after the last dose of investigational product (whichever comes first). Individualized Follow-up visits will be scheduled every 12 weeks. Subjects who withdraw from treatment will also enter the Individualized Follow-up Period, unless the subject also withdraws consent.

An independent data monitoring committee (IDMC) will evaluate risks relative to benefits through review of safety and efficacy data on an ongoing basis during the study. Any case of suspected or confirmed PML will go through independent PML adjudication and an opinion will be provided to the sponsor.

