12. SAFETY ANALYSES

All safety analyses will be performed for the Safety population as defined in Section 6.4. These data will not undergo any inferential statistical analysis. All safety analyses described below will be performed on data collected through the Week 60 study visit for the primary safety. The safety data from individualized follow-up period will be listed for any data available.

Section 9.2.1 details the algorithm for deriving baseline values. In the event that a baseline value for an assessment cannot be derived for a subject, the subject will be excluded from the change from Baseline analysis for that assessment; however, the subject's data will still be included in visit assessment summaries and analyses.

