12.6.1. Immunogenicity

A by-visit summary will present descriptive statistics for the actual and change from Baseline results by visit and treatment group for IgG, IgA, IgM, HAHA, high sensitivity C-reactive protein (hsCRP), and B-lymphocyte chemokine (BLC). Additionally, descriptive statistics will be used to summarize each subject's largest decrease from Baseline. The number and percentage of subjects below the LLN at each visit, below the LLN at any time during the on-therapy period and below the LLN during the first 12 weeks of treatment will be presented by treatment group.

All immunogenicity data will be presented in a data listing.

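### On-therapy ends on the planned Week 60 day, and a later Week 60 record of a subject entering Individualized Follow-up is sent to an analysis visit that Table 9-1 does not contain

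*SAP*

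**What the plan says.** SAP Section 9.3.2 defines on-therapy as "on or after the start date of study medication and on or before 4 weeks after the date of last dose". It is written for dated events such as adverse events and medications. Anything later is follow-up for a subject who does not enter IFU and individualized follow-up for one who does.

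SAP Section 9.3.3 carries the rule over to visit data: "Determine the therapy period and study day for all records using the algorithms from Section 9.3.1 and Section 9.3.2". Each period then has its own slotting instruction. The IFU one begins "For records determined to be during the individualized follow-up period, use the study day with the slotting intervals in the table below" and ends by naming an IFU analysis visit. Table 9-1 stops at Week 60 (days 401 to 428) and has no IFU row, although protocol Table 6-2 schedules such visits from Week 72.

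On timing, SAP Section 3 states: "After the last dose of ofatumumab SC or placebo at Week 56, subjects will be followed-up for a minimum of 4 weeks". The note to protocol Table 6-1 adds: "Visits from Week 2 through Week 60 to be scheduled within ±3 days of the specified time point".

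On reporting, SAP Section 12 bases the safety analyses on data up to the Week 60 visit, but also says: "The safety data from individualized follow-up period will be listed for any data available". SAP Section 10.1 runs the core period to the Week 60 visit or early discontinuation. SAP Section 12.6.1 counts subjects with values "below the LLN at any time during the on-therapy period".

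**The concern.** The cut-off has no tolerance at the one visit that is planned to fall on it. A Week 60 visit can be on schedule under the protocol and still fall outside on-therapy. What happens next depends on a fact unrelated to the date. If the subject does not enter IFU, the record is follow-up, and the Week 60 row, which Table 9-1 footnotes as the follow-up visit, can take it. If the subject enters IFU, the same record is pointed at a row that does not exist, and Section 12 would only list it. Yet Section 12 also says that data up to Week 60 are analysed, so one record meets both rules.

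The split is not neutral. For completers outside the extension study, IFU entry turns on whether B cells and IgG have recovered at Week 60. The Week 60 result therefore helps decide whether that result is summarised. On the literal reading, the late records removed are those of subjects who had not recovered, which would make the Week 60 B-cell and immunoglobulin summaries look closer to recovery than they are. With 69 subjects randomized, a few lost records can matter.

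**Working it through.** **Inputs**
- On-therapy ends at last dose + 28 days, inclusive (SAP 9.3.2).
- Last dose planned at Week 56, next visit Week 60 (SAP 3).
- Visit window ±3 days (protocol Table 6-1 note).
- First dose is Day 1, so Week w falls on day 7w + 1 (SAP 9.3.1).
- Week 60 row: target day 414, interval 401 to 428 (SAP Table 9-1).
- Distribution of actual visit dates: not given, so assumed below.

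**Where the boundary falls**
- Week 56: 7 × 56 + 1 = 393. End of on-therapy: 393 + 28 = 421.
- Week 60: 7 × 60 + 1 = 421. The boundary is the planned visit day.
- Table 9-1 does not reproduce these days: it gives 386 and 414, each 7 days earlier. Its spacing does agree (386 + 28 = 414), so the coincidence holds on either scale. The 7-day shift is a separate matter.
- A Week 60 visit within ±3 days falls on days 418 to 424, inside 401 to 428. Study day alone therefore returns Week 60 for every on-schedule visit.

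**Share of Week 60 records past the boundary, for subjects dosed at Week 56**

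If only the Week 60 date varies, the share is the probability of a positive offset. If the Week 56 and Week 60 offsets vary independently with the same distribution, it is (1 − P(equal offsets)) / 2, and the gap runs from 28 − 6 = 22 to 28 + 6 = 34 days.

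| Assumed dates | Only Week 60 varies | Both vary |
|---|---|---|
| Uniform over ±3 days | 3/7 = 42.9% | 21/49 = 42.9% |
| Triangular (weights 1,2,3,4,3,2,1) | 6/16 = 37.5% | 41.4% |
| 50% exactly on day, rest spread evenly | 25% | 35.4% |
| 90% exactly on day, rest spread evenly | 5% | 9.4% |
| Skewed early (weights 7 down to 1) | 6/28 = 21.4% | not computed |
| Skewed late (weights 1 up to 7) | 18/28 = 64.3% | not computed |

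Any symmetric pattern gives between 0% and 50%. If sites took the four-week minimum literally and used only offsets 0 to +3, uniformly, the share would be 3/4 = 75%.

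**Skipped Week 56 dose**

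The last dose is then at Week 52, day 365. An on-schedule Week 60 visit is 421 − 365 = 56 days later (50 at the least, with both windows used), so 100% of such records are outside on-therapy.

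**What happens to a late Week 60 record**

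| | Does not enter IFU | Enters IFU |
|---|---|---|
| Period under 9.3.2 | Follow-up | Individualized follow-up |
| Literal slotting under 9.3.3 | Week 60 row | IFU visit, no row in Table 9-1 |
| Slotting by study day alone | Week 60 | Week 60 |
| On-therapy count in 12.6.1 | Not counted | Not counted |

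An Early Withdrawal visit more than 28 days after the last dose meets the same gap. Literally it is an IFU record, while its study day would normally fall in an existing row.

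**The case against.** The best reply is that the SAP can be read so that nothing is lost. Section 9.3.3 opens by placing records at visits the protocol specifies, every post-baseline instruction uses study day with the table's intervals, and the Week 60 interval covers all on-schedule visits. Section 10.1 puts Week 60 inside the core period, Section 3 places IFU after it, and Section 12.6 summarises laboratory data at each assessed time point without an on-therapy restriction. This stands as far as it goes: the outcome is ambiguous, not certain. It does not settle the matter, because Section 9.3.3 also requires the therapy period and names a separate IFU analysis visit. Two programmers could reach different Week 60 counts.

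Four stronger inferences are tempting and are not supported:
- **That 43% of Week 60 records are lost.** The figure needs uniform dates. Protocol Section 6 asks for visits as close as possible to plan, which points to a lower share, and the loss arises only on the literal reading and only for IFU entrants.
- **That the loss falls on ofatumumab and hardly on placebo.** The predicted median repletion of about 28 weeks (protocol Section 3.3) makes this likely among completers. But withdrawals from treatment in either arm also enter IFU, and no split by arm is given.
- **That the end-of-treatment visit is depleted.** The Table 9-1 footnote makes Week 56, not Week 60, the end-of-treatment visit.
- **That the below-LLN on-therapy count is distorted in one arm by rule.** The 28-day cut-off removes late Week 60 samples in both arms, and a subject already low at an earlier on-therapy sample is still counted.

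**Conclusion.** The point holds as a conflict between SAP Sections 9.3.2, 9.3.3, 10.1, 12 and Table 9-1. The boundary coincides with the planned Week 60 day, and a late Week 60 record is handled according to IFU entry, for which the table has no visit. On the literal reading, late Week 60 records of subjects with unrecovered B cells or IgG leave the by-visit laboratory, immunoglobulin, B-cell and vital-sign summaries. On the study-day reading they stay.

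The size cannot be fixed from the documents, which give neither visit dates, nor the number of completers, nor IFU entry by arm. The 43% is conditional on uniform dates; the share could be 5% to 9% if visits are mostly exact, and above half if they run late.

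The scope is limited. The co-primary endpoints are derived from dates, the Week 56 summaries are unaffected for subjects dosed at that visit, and safety data receive no inferential test. It should be corrected, because the rule is stated rather than merely missing and the possible selection depends on the outcome being summarised.

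**What to change.** In SAP Sections 9.3.2 and 9.3.3, separate visit-based data from event classification:
- Define the core period for visit-based data as first dose through the Week 60 or Early Withdrawal visit, inclusive.
- Start IFU on the day after that visit.
- Slot core records by study day alone.
- Use the same end for the on-therapy counts in Section 12.6.1.

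The 28-day treatment-emergent rule for adverse events can stay.

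The cost is about two sentences and a small programming change. The downside is that a few records up to about 6 days past the 28-day mark count as core-period data, and later ones do where the last dose was skipped or the withdrawal visit was late.
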